Name of project	Validation of AVAS classification by using machine learning in prediction of vascular access creation and in the prediction of uninterrupted use of the vascular access for dialysis
Acronym of the project	VAVASC trial (Validation of the Arterio Venous Access Stage Classification) trial
Web page	www.vavasc.com
ClinicalTrial identifier	NCT04796558
Leader of the project	[name], [name], [name],
Type of the study	Prospective, multi-centre, international, collaborative
Registration	None
Number of patients included	Minimum 500, optimal 1000
Start of the study	2021
Estimated end of the study	2023-2024
Ethics committee approval	
Yes. This should be reviewed in each centre, and if necessary each centre should have approval of its own ethics committee.
 
However, please note that this is an observational study that is collecting data from existing medical records. In many centres (e.g. those with routine ultrasound arteriovenous mapping) there will be no alteration to patient care. There is therefore unlikely to be a requirement for patient information or consent.
 
If ethical approval is required in individual centres it could potentially be obtained from a Proportionate Review Service. If applicable, participating units should also register with local audit/clinical governance structures and gain permission from the Caldicott Guardian.

Informed consent	Depends on the centre and decision of the ethical board of each centre
Database (data storage)	Electronic database - eCRF ([name])
Statistic analysis	Predictive modelling by using machine learning ([name], [name])
Financial support	No


Background
	
Ultrasound of upper limb vessels as a part of preoperative assessment of patients referred for arteriovenous access placement has been recommended repeatedly in several studies and guidelines. Each patient needing arterio-venous access (AVA) is unique and has different possibilities for fistula creation that depend on many factors as well the anatomical condition of inflow arteries and outflow veins, the so-called ‘arteriovenous access map’. In 2020 we created, published and retrospectively evaluated the inter-rater reliability of the AVAS classification, which is a simplified way of sharing the information about suitability for access creation depending on vascular anatomy (doi: 10.1093/ckj/sfaa189).
 
However, before routine use of the AVAS classification system in clinical practise it requires prospective validation and comparison with other clinical factors. Finally, whether the AVAS classification can be used for the prediction of vascular access function as defined by uninterrupted use of vascular access for dialysis without need for any access intervention/procedures (SONG-HD, doi: 10.1053/j.ajkd.2017.12.003) remains to be tested.
 
This project has two main parts:
 
 1. Validation of AVAS classification with and without combination with other factors using a predictive statistical model. 2. Validation of AVAS classification in terms of prediction of uninterrupted use of successfully created vascular access for dialysis. 
The data will be collected prospectively. Both parts of the project will be taking place simultaneously.

Working hypothesis
	
Part 1: AVAS classification with/without selective clinical parameters is a useful tool for sharing information about the type of AVA which will be created.
 
Part 2: Increasing AVAS with/without selective clinical parameters is an accurate predictive tool for the prediction of the uninterrupted use of successfully created vascular access for dialysis.


Socio Economic aspect
	
Classification of vascular access is important for improving efficiency of communication across multi-disciplinary teams, which helps streamline care and avoids errors.
 
At the individual patient level it is critical for communicating vascular access complexity and thus ensuring preservation of precious access.
 
At a unit level, in the NHS best practice tariff criteria are based on national guidance and expert opinion that are intended to drive improvements in processes of care.
 
The best practice tariff for haemodialysis is that 80% of patients on haemodialysis should receive dialysis via a functioning arteriovenous fistula.
 
Individual units with complex vascular access populations may be unfairly penalised for not meeting this target. A classification system for vascular access would help define vascular access populations, leading to fairer comparison of unit performance and appropriate remuneration for the cost of care.
															

Methodology
	
Data will be collected prospectively (Belfast City Hospital, UK, University hospital Královské Vinohrady Prague CZ). Other centres around the world will be asked for cooperation (announcement will be posted via scientific societies, Twitter, ResearchGate, LinkedIn, Facebook, Kidney Academy etc.) in March 2021. The data collected will be the parameters of the vessels on the upper limb, in order to be able to evaluate AVAS (VAVASC FORM). Along with anatomical dispositions of the patients, other parameters will be collected.
 
Obligatory parameters (parameters A):
 
 
 - Side of the arm:	Left	Right	
 
 - Dominant hand:	Left	Right	
 
 - Allen's test:	Positive	Negative	
 
 
(A negative Allen’s test is demonstration of a complete palmar arch and intact collateral blood flow to the hand)
 
 
 - Sex:	M	F	
 
 - Age:	.....	
 
	- Side of the arm:	Left	Right	- Dominant hand:	Left	Right	- Allen's test:	Positive	Negative	- Sex:	M	F	- Age:	
- Side of the arm:	Left	Right														
- Dominant hand:	Left	Right														
- Allen's test:	Positive	Negative														
- Sex:	M	F														
- Age:															

	
 - Height: - Weight: - BMI: - Diabetes: Yes No - CV line previous or current Yes No - Side of the CV line if place Left Right 
Non-obligatory parameters (parameters B):
 
 - Smoking history: Yes No - Hypertension: Yes No - Heart failure: Yes No - Ischemic heart disease: Yes No - Cancer (previous or current): Yes No 
In order to evaluate uninterrupted use of the vascular access for dialysis (part 2 of the study), we will follow the patients and do a time to event analysis of the arteriovenous accesses for one year after creation or up until the first intervention for maintaining patency has been performed. If the patient dies during follow up the date of death should be recorded. The data for this part will be collected prospectively (Belfast City Hospital, UK, University hospital Královské Vinohrady Prague, CZ and other centres).
 
Predictive models will be used for validation of AVAS classification. The data will be registered via eCRF and analysed by [name] and [name]

Methodology step-by-step
	
 1. Patient with need of AVA creation is assessed in outpatient clinic as usual. 2. To reduce bias all consecutive patients must be captured. 3. Each registered health care professional (HCP) in the participating centre in the VAVASC study has access to eCRF (electronic database). They can fill the collected data straight into the database or at a later date from the notes they usually take when recording arteriovenous mapping. If the HCP or centre prefers paper forms, a paper document (VAVASC FORM) can

	
be used and researchers from each centre will put the data from the paper form into the eCRF regularly. Collection of data into eCRF primarily is the preferable approach. If the HCP examining the patient has access to eCRF, they do not have to fill the paper VAVASC FORM.
 
4. Patient is scanned using ultrasound and the vascular parameters are marked/registered (eCRF or VAVASC FORM). If the HCP wishes, they can evaluate the patient according to AVAS classification. The HCP can skip this step since the vascular parameters can be used to establish the AVAS by the VAVASC research group.5. Patients' risk factors are also marked/registered. Only “obligatory parameters” (parameters A) are necessary to collect. The HCP can also collect the parameters B, that are voluntary. 
For centres using paper form (VAVASC FORM)
 
- If the centre/individual HCP prefers paper forms only, VAVASC FORM is stored in a prepared box in each clinic in the hospital entitled as “VAVASC”.- Researcher from each centre regularly collects the VAVASC FORM documents.- Researcher from each centre regularly enters obtained data from VAVASC FORM into the eCRF.- A similar approach may be used by centres that already record the information on the VASVASC form elsewhere (e.g. the medical records or centre specific arteriovenous maps) 
6. Patient is indicated for AVA as usual (not necessarily as is indicated by AVAS)7. Researcher from each centre regularly follows up the patients and enters type of AVA which was created into the eCRF.8. Researcher from each centre regularly follows up the patients and enter data about the fate of AVA for one year or up until the first intervention for maintaining
--	---

	patency has been performed. If the patient dies during follow up the date of death should be recorded.
Statistic method	Predictive modelling using machine learning ([name], [name])
Responsibilities of the research team	
 1. The centre lead registers interest with VAVASC research group, and will seek local ethical approval. 2. Centre lead is responsible for ensuring the required data is collected by HCPs in the clinic, and supervising the data collectors in their centre. 3. HCP in the clinic: Carries out arteriovenous mapping and records clinical data. 4. HCP in the clinic or data collector fills the paper VAVASC FORM/ or fills the data into eCRF (computer) database, approx. 10 minutes. 5. Data collector in each centre where eCRF is not used: may collect the VAVASC FORM and enter data into the eCRF, approx..1 hour/week 6. Centre lead or data collector in each center regularly checks the patient follow up, approx. 1 hour/week 7. Project leader of VAVASC group: regularly sends informative email about status of the study to all researchers (how many patients recruited, how many centres are active etc.). 8. VASVASC group will analyse results and prepare manuscript.
Authorship	
Named author is a HCP who acts as a centre lead, and sets up the study in their centre including ethical approval. This HCP is also invited into the writing group, so they are able to participate in drafting and reviewing the final manuscript.
 
Collaborator /collaborative author (also PubMed citable) is a HCP who collects patient data and enters the data in the eCRF or provides the data to the centre lead for entry. To reduce bias collaborators must capture consecutive patients. There is no minimum or maximum amount of consecutive patients that could be entered by a collaborator. However, each collaborator must collect data for patients who have

	
gone onto have successful vascular access creation and these patients must be followed up for the full follow up period. Unfortunately, in some cases attempts at vascular creation will fail so collaborators are encouraged to recruit as many consecutive patients as they can. To avoid disadvantaging and excluding low volume centres (which would impact the generalizability of the study) no time limit will be set for recruitment of consecutive patients. However, the eCRF will close to further data entry on X.

--	---

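### Part 2 follows successfully created accesses from creation but does not say when success is judged and names only a patency intervention as the event, so early failures can go uncounted

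*Protocol*

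**What the plan says.** **Population.** The Background describes Part 2 as the "prediction of uninterrupted use of successfully created vascular access for dialysis". The Part 2 working hypothesis repeats the restriction: AVAS "is an accurate predictive tool for the prediction of the uninterrupted use of successfully created vascular access for dialysis".

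**Outcome concept.** The Background takes access function to be "uninterrupted use of vascular access for dialysis without need for any access intervention/procedures".

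**Time zero and event.** The Methodology row plans the following: "time to event analysis of the arteriovenous accesses for one year after creation or up until the first intervention for maintaining patency has been performed". Step 8 of the step-by-step row repeats the one-year limit and the stop at first intervention, and asks centres to record the fate of the access. Date of death is also recorded.

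**Who must be followed.** Step 2 requires consecutive capture. The Authorship row requires each collaborator to contribute patients who have "gone onto have successful vascular access creation and these patients must be followed up for the full follow up period", and adds that "in some cases attempts at vascular creation will fail".

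Nothing in the protocol defines successful creation, says when it is judged, or says how an access lost early without an intervention is to be counted.

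**The concern.** Entry to Part 2 depends on a success that has no stated time, while the clock starts at creation. If a centre judges success at the end of the operation, entry and clock agree. If it judges success weeks later, entry depends on something that happens after time zero, and early losses leave the cohort.

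The event wording adds a second gap that remains even when success means technical success. An access that thromboses and is given up without any attempt to restore it has plainly not delivered uninterrupted use. Yet it has had no intervention to maintain patency, which is the only event named.

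By either route, early failures may not be counted. AVAS summarises preoperative vessel anatomy, so early failure is a plausible place for it to discriminate, and these are the outcomes Part 2 would lose. Centres are recruited internationally by open announcement, so the handling may also differ between them.

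**Working it through.** The plan states no figure for this point: 500 to 1000 patients are sought, without event rates. The check is therefore a reading of the text followed by an illustration on assumed rates.

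**Reading.** Take an access created on day 0 that clots in week 2 and is abandoned without intervention.

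- *Success judged later than the operation.* The access is a failed attempt. The Authorship row's full-follow-up duty does not reach it, and it is outside the population in the Background and hypothesis.
- *Success judged at the operation.* The access is in the cohort from day 0. The named event, "up until the first intervention for maintaining patency has been performed", never occurs. As written, it is censored or carried event-free.
- *Outcome concept in the Background.* Uninterrupted use was not achieved, so this should be a failure.

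The first two lines both conflict with the third.

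**Illustration.** Assume two equal AVAS groups, favourable and unfavourable, with early failure risk f and later event risk r among accesses that survive the early period. All values are assumptions.

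- Early failures counted: one-year risk = f + (1 − f) × r.
- Early failures dropped: one-year risk = r.
- Share of events lost = sum of the two f values ÷ sum of the two one-year risks with early failures counted.

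Example with f of 10% vs 30% and r of 30% in both:

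- Counted: 0.10 + 0.90 × 0.30 = 0.37 and 0.30 + 0.70 × 0.30 = 0.51, a difference of 14 points.
- Dropped: 30% vs 30%, a difference of 0.
- Events lost: 0.40 ÷ 0.88 = 45%.

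| Early failure f | Later risk r | Counted (difference) | Dropped (difference) | Events lost |
|---|---|---|---|---|
| 5% vs 15% | 30% vs 30% | 33.5% vs 40.5% (7) | 30% vs 30% (0) | 27% |
| 10% vs 30% | 30% vs 30% | 37% vs 51% (14) | 30% vs 30% (0) | 45% |
| 20% vs 40% | 30% vs 30% | 44% vs 58% (14) | 30% vs 30% (0) | 59% |
| 5% vs 15% | 30% vs 40% | 33.5% vs 49% (15.5) | 30% vs 40% (10) | 24% |
| 10% vs 30% | 30% vs 40% | 37% vs 58% (21) | 30% vs 40% (10) | 42% |
| 20% vs 40% | 30% vs 40% | 44% vs 64% (20) | 30% vs 40% (10) | 56% |
| 20% vs 20% | 20% vs 40% | 36% vs 52% (16) | 20% vs 40% (20) | 45% |

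The last row shows the opposite direction: with equal early failure, dropping it enlarges the difference.

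**Overall uninterrupted use.** In the first three rows the average one-year event risk with early failures counted is 37%, 44% and 51%, so uninterrupted use is 63%, 56% and 49%. Dropping early failures gives 70% each time, an overstatement of 7, 14 and 21 points.

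**Kept without an event.** If early failures are censored at abandonment, before the later events, the estimates match the dropped columns. If all are carried event-free to one year, an extreme case, the risk is (1 − f) × r. For f of 10% vs 30% and r of 30% this gives 0.90 × 0.30 = 27% and 0.70 × 0.30 = 21%, so the unfavourable group looks better.

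**The case against.** The best defence is that success qualifies creation, not function. The Background treats the two separately, the protocol never mentions maturation or first cannulation, and the sentence on failure speaks of attempts at creation. On that plain reading an access is successful once made, and entry and time zero coincide. The operative steps carry no success filter: consecutive patients are captured, the type of access is recorded, and its fate is followed for a year. The Authorship row sets conditions for credit, not the analysis population. Exact event coding could also sit in a statistical analysis plan that is not at hand.

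Much of this stands. Technical success is the natural reading, and recording fate means that data on early losses may well exist. A reader might infer that the protocol orders early failures to be excluded; it does not, it only leaves room for it. A reader might also infer that the weeks before success is declared are necessarily event-free. That fails too, because an access can have a patency intervention and later be declared successful.

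Two things are not answered. The Authorship row is where the protocol states a full-follow-up duty in terms of success, and a later analysis plan cannot recover follow-up that a centre did not collect. And the plain reading does not help an access abandoned without intervention, because the named endpoint still misses it.

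**Conclusion.** The point holds as an ambiguity in cohort entry combined with an endpoint narrower than the stated outcome. The text permits early failures to go uncounted but does not require it.

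The consequence for the overall rate is clear in direction: where early failures are not counted, one-year uninterrupted use is overstated. For the AVAS association, attenuation is the usual result if early failure rises with AVAS stage. It would be tempting to conclude that the bias is always toward the null or abolishes the association. The documents do not support that: the fall to 0 comes from assuming equal later risk, a 10-point difference survives when later risk is 30% vs 40%, and equal early failure can enlarge the difference. All sizes rest on assumed rates. The finding itself rests on the wording.

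It should be corrected, because it affects the Part 2 result under either reading of success and is cheap to settle.

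**What to change.** In the Methodology row and in step 8, state that:

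1. success is judged at the end of the creation procedure;
2. every access so created enters Part 2 from that date;
3. any later loss (thrombosis, abandonment, or never becoming usable) counts as an event alongside the first patency intervention, with a stated rule for dating a loss that has no obvious date.

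The Authorship row should refer to the same definition, so that the follow-up duty covers every access that enters Part 2. An analysis limited to accesses that reached dialysis use may be kept as secondary, with its clock starting at first use.

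The cost is a few sentences, a short dating rule for accesses that never become usable, and a somewhat less favourable uninterrupted-use rate. No extra patients or visits are needed.

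### Part 2 targets uninterrupted dialysis use without any access procedure, but its stated rule runs from creation to the first patency intervention and contains no use criterion

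*Protocol*

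**What the plan says.** **Target.** The Background row of the protocol describes "vascular access function as defined by uninterrupted use of vascular access for dialysis without need for any access intervention/procedures" and says that whether AVAS predicts it remains to be tested. The Part 2 working hypothesis is that AVAS, with or without clinical parameters, is an "accurate predictive tool for the prediction of the uninterrupted use of successfully created vascular access for dialysis".

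**Rule.** The Methodology row says that, for the purpose of evaluating uninterrupted use, patients will be followed and analysed as follows: "time to event analysis of the arteriovenous accesses for one year after creation or up until the first intervention for maintaining patency". Step 8 of the step-by-step methodology repeats the same window for data entry, asking the local researcher to "enter data about the fate of AVA for one year or up until the first intervention for maintaining", where the thing maintained is again patency. Date of death is also to be recorded.

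**Who enters.** Step 1 reads "Patient with need of AVA creation is assessed in outpatient clinic as usual". It does not mention dialysis status.

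**What else is recorded.** The obligatory and voluntary parameters are limb, demographic and comorbidity items. Step 7 adds the type of access created. None of the named items is dialysis status, date of first use or date that use ended. The Authorship row refers to patients who have "gone onto have successful vascular access creation" and contrasts them with failed attempts, but gives no criterion for success.

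**The concern.** The protocol names one outcome and then fixes a rule that, read as written, measures another. Two things are lost between them.

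1. **Use.** The target is about an access being used for dialysis. The rule starts its clock at creation and stops it at a patency intervention or at one year. Nothing in it asks whether the access was ever used.
2. **Scope of the event.** The target excludes every kind of access procedure. The rule names only interventions that serve to maintain patency.

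At stake is what one of the study's two main parts can conclude. An analysis that follows the rule estimates intervention-free survival from creation. Reported as uninterrupted use, its event-free share may include accesses that never delivered a dialysis session, and readers could not tell how many.

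**Working it through.** The protocol gives no event rate, effect size or power for Part 2, so there is no figure to reproduce. The check is a comparison of the texts, followed by a sensitivity range.

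**Step 1: compare target and rule.**

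| Element | Target (Background, Working hypothesis) | Rule (Methodology; step 8) |
|---|---|---|
| Time origin | Not stated; concerns use for dialysis | Creation of the access |
| Use for dialysis | Required | Not mentioned |
| Ending event | Any access procedure | First intervention to maintain patency (implied) |
| Horizon | Not stated | One year |

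**Step 2: apply the rule literally**, with the patient alive at one year.

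- Never used, no patency intervention: could be counted event-free; not uninterrupted use under the target.
- Used, then abandoned without a patency intervention: could be counted event-free; use was interrupted.
- Used, with a procedure done for another reason: no event under the rule; an event under the target.
- Used all year, no procedure: event-free under both.

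The first three cases cannot be told from the fourth.

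**Step 3: size of the first case.** Let u be the share of accesses in the Part 2 analysis that are never used within the year, and g the share of those with no patency intervention. The share counted event-free without use is u × g. Both inputs are assumptions; the protocol gives neither. The range for u starts at 0 because the restriction to successfully created accesses might remove every never-used one.

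| u | g = 0.5 | g = 1.0 |
|---|---|---|
| 0% | 0 points | 0 points |
| 10% | 0.10 × 0.5 = 5 points | 0.10 × 1.0 = 10 points |
| 20% | 0.20 × 0.5 = 10 points | 0.20 × 1.0 = 20 points |
| 30% | 0.30 × 0.5 = 15 points | 0.30 × 1.0 = 30 points |

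The range is therefore 0 to 30 points. It ignores deaths and covers never-used accesses only. Abandonment after use and procedures done for other reasons would come on top, and the protocol offers no basis for sizing them. The planned 500 to 1000 counts patients, not accesses in the Part 2 analysis, so I give points rather than numbers of accesses.

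**Step 4: can a direction be given for the AVAS association?** Assume two AVAS groups with 65% and 50% event-free among used accesses. Leaving never-used accesses out, the odds ratio is (0.65/0.35)/(0.50/0.50) = 1.86. Under the rule, the event-free share in each group is (1 − u) × p + u × g, where p is that group's event-free share among used accesses. Take g = 1:

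- u = 20% and 30%: 0.80 × 0.65 + 0.20 = 0.72 and 0.70 × 0.50 + 0.30 = 0.65. The odds ratio is (0.72/0.28)/(0.65/0.35) = 1.38, below 1.86.
- u = 30% and 20%: 0.70 × 0.65 + 0.30 = 0.755 and 0.80 × 0.50 + 0.20 = 0.60. The odds ratio is (0.755/0.245)/(0.60/0.40) = 2.05, above 1.86.

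The sign depends on which group has more non-use, which the protocol does not tell us. These sums show only that no direction can be asserted; they do not estimate a bias.

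**The case against.** **The sentence sets a follow-up window, not an endpoint.** It can be read as saying how long each access is observed, with event coding left to a SAP that is not shown. Part of this stands: the event is implied, not defined, so I say that such accesses could be counted event-free, not that they will be. But the sentence names the analysis, its origin, its horizon and the only occurrence that ends it, and it is introduced as the means of evaluating uninterrupted use. A SAP could add detail, but the protocol's own sections would still disagree.

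**The undefined terms may already close the gap.** If a successfully created access must be usable, some or all never-used ones leave Part 2. The fate of the access, which step 8 asks for, could cover use or abandonment, and the eCRF may hold such fields. This stands as a limit on size, and is why u starts at 0. It does not supply a use criterion, because none is stated.

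**The two event phrases may be meant as the same thing.** Possibly; if so, aligning the wording settles that half of the point.

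**Stronger readings to avoid.** A reader might infer that use data are not collected, that many accesses in Part 2 will be unused, or that the AVAS association will be biased in a known direction. The documents support none of these: the eCRF is not shown, no rate of non-use is given, and step 4 of the working moves either way. Nor is the absence of detailed definitions a fault in itself, since a SAP may supply them.

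**Conclusion.** The point holds as an internal inconsistency. The Background and the Part 2 hypothesis promise uninterrupted dialysis use free of any access procedure; the Methodology row and step 8 describe a creation-based rule with no use component and a narrower event. Followed literally, Part 2 would estimate intervention-free survival from creation under another name.

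The size is unknown from the document. Under the assumed ranges, never-used accesses would add between 0 and 30 percentage points to the event-free share, and zero is possible. The textual conflict does not depend on those assumptions; the practical harm does. It also depends on what the unseen eCRF records and on how successful creation is judged.

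**What to change.** Reconcile the Background, the Methodology row and step 8 so that they describe one outcome.

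- **Event:** use the Background's scope, "uninterrupted use of vascular access for dialysis without need for any access intervention/procedures", in place of the narrower patency wording.
- **Use:** record the date of first dialysis use of this access (or that it was never used) and the date that use ended. The Ethics committee approval row says "this is an observational study that is collecting data from existing medical records", so these dates may be obtainable there.
- **Scoring:** do not count never-used or abandoned accesses as uninterrupted use.
- **Existing analysis:** keep the creation-based analysis, labelled as intervention-free survival from creation.
- **Fallback:** if use cannot be recorded, rename the Part 2 outcome and hypothesis to that label.

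The cost is a few extra follow-up fields and some rewording. The study reports no financial support and allows about one hour a week per centre for follow-up checks, so some centres may find dialysis dates harder to obtain. Renaming alone costs only wording, but Part 2 would then reach a narrower conclusion and would not answer the question about use.

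### Part 1 names only fitted models to validate a published classification; an unfitted table of AVAS-indicated against created access should be reported beside them

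*Protocol*

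**What the plan says.** The Background section describes AVAS as an existing scheme: "In 2020 we created, published and retrospectively evaluated the inter-rater reliability of the AVAS classification". It sets Part 1 as validation of AVAS "with and without combination with other factors using a predictive statistical model". The Working hypothesis for Part 1 is that "AVAS classification with/without selective clinical parameters is a useful tool for sharing information about the type of AVA which will be created".

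The method is given in the same terms wherever it appears. The last paragraph of the Methodology says "Predictive models will be used for validation of AVAS classification". The Statistic method entry reads "Predictive modelling using machine learning", and the Statistic analysis entry in the opening table says the same in almost the same words.

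Three items in Methodology step-by-step bear on this:

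- Step 4 lets the clinician skip the AVAS assessment, because "the vascular parameters can be used to establish the AVAS by the VAVASC research group".
- Step 6 reads "Patient is indicated for AVA as usual (not necessarily as is indicated by AVAS"), so AVAS carries an indication of its own and departures from it are expected.
- Step 7 records the type of access created.

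The protocol nowhere says that the indicated access will be compared directly with the created one. The statistical analysis plan is not shown.

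**The concern.** Validating a fixed scheme and fitting a model that uses the scheme as an input answer different questions. Someone who is handed an AVAS stage reads it by its published meaning. A model fitted on stage ignores that meaning and predicts whichever access was most often created in the stage in this study. If a stage indicates one access and usually receives another, the model corrects the mismatch without showing it.

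A favourable model accuracy could then be reported as validation of AVAS although the published indication for a whole stage did not match practice. The Background makes prospective validation a precondition for routine use, so this distinction should be visible in the results.

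**Working it through.** **Inputs.** From the protocol: a minimum of 500 patients and an optimum of 1000, with no derivation; no stage shares, expected agreement or target accuracy. There is thus no planned accuracy figure to reproduce, and every rate below is an assumption for illustration.

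**Two measures.** Let w_s be the share of patients in stage s and, for this illustration only, let each stage indicate one access.

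- AVAS's own agreement: sum over s of w_s × P(indicated access | s).
- Expected accuracy of a model on stage alone that has learned the commonest access in each stage: sum over s of w_s × max over k of P(access k | s).

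The terms differ only in stages where the indicated access is not the commonest.

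**Assumed example.** Stage shares are 40/35/25%. The indicated access is created in 75%, q and 80% of the three stages. In the middle stage one rival access is created in 95% − q.

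- Agreement = 0.40×0.75 + 0.35×q + 0.25×0.80 = 0.50 + 0.35q.
- Fitted = 0.50 + 0.35×max(q, 0.95 − q).
- The gap closes at q = 0.95 − q, that is q = 47.5%.

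| q | Rival | AVAS agreement | Fitted, expected | Gap (points) | Fitted, 10-fold cross-validated, n = 500 |
|---|---|---|---|---|---|
| 25% | 70% | 58.75% | 74.50% | 15.75 | 74.5% |
| 35% | 60% | 62.25% | 71.00% | 8.75 | 71.0% |
| 45% | 50% | 65.75% | 67.50% | 1.75 | 67.0% |
| 50% | 45% | 67.50% | 67.50% | 0 | 66.9% |
| 55% | 40% | 69.25% | 69.25% | 0 | 69.1% |
| 75% | 20% | 76.25% | 76.25% | 0 | 76.2% |

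The last column is simulated. Near the tie the cross-validated model loses about half a point, because some training folds pick the wrong access. At q = 50% it falls slightly below AVAS's own agreement (66.9% against 67.4% in the same simulation).

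**Second set of assumptions.** Shares are 50/30/20%, the indicated access is created in 90% of the first and third stages, and a fraction r of the middle stage receives another access. Agreement = 0.45 + 0.30×(1 − r) + 0.18; fitted = 0.63 + 0.30×max(r, 1 − r).

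- r = 0.3: 84% for both.
- r = 0.6: 75% against 81%.
- r = 1.0: 63% against 93%.

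Simulation with 10-fold cross-validation at n = 500 and n = 1000 agrees within a point. Cross-validation does not remove the gap, because its source is the relearned mapping and not overfitting.

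**Precision of direct agreement.** The 95% half-width is 1.96×√(p(1 − p)/N). At p = 70% it is 4.0 points for N = 500 and 2.8 for N = 1000. For one stage holding 25% of 500 patients (125), it is 1.96×√(0.21/125) = 8.0 points. The planned size supports the overall figure well and the per-stage figures more coarsely.

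**The case against.** The strongest case against is that the protocol says models will be used, not that nothing else will be. It names no performance measure, and a stage-by-access table is the kind of detail an analysis plan can supply. That stands in part: nothing in the protocol blocks the comparison. But the protocol does more than stay silent. It names the validation method in several places, always as predictive modelling.

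Three stronger readings are tempting, and the document does not support them.

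- A reader might infer that a fitted model always flatters AVAS, or can never score below it. The inequality holds for expected accuracy once the commonest access per stage is known. It does not hold for cross-validated accuracy, as the q = 50% row shows, and there is no gap at all when the indicated access is the commonest in every stage.
- A reader might infer that each stage indicates exactly one access. The protocol never defines the stages or their mapping. Step 6 shows only that AVAS indicates something. If a stage allows several accesses, agreement must be scored against the set, and the one-access formula does not apply as written.
- A reader might infer that the models are the wrong method and should be made secondary. The Part 1 hypothesis concerns sharing information, with or without clinical parameters. Whether stages carry information about the access created is a proper question for a fitted model, and the combination with clinical factors needs one.

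Disagreement would also not prove the AVAS indication wrong: patients are treated as usual, so it may reflect local practice.

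**Conclusion.** The point holds in a limited form. The only validation method named for Part 1 can show that AVAS stages separate patients by access type. Alone, it cannot show whether the access that AVAS indicates is the one created, and it would not reveal a stage where the two diverge.

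How large the divergence is in this study cannot be known from the protocol. Under the first set of assumptions the overstatement is between 0 and about 16 points. The upper figure needs a rival access in 70% of one stage, and nothing in the document suggests that any stage lies on that side of the crossover. Under the second set it reaches 30 points (93% against 63%), but only if an entire stage receives another access. Both illustrations assume one indicated access per stage. This is a cheap improvement to the plan, not a fault that must be repaired before the study can be interpreted.

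**What to change.** Add to the Methodology that, alongside the predictive models, Part 1 will report the unfitted comparison of the access, or set of accesses, indicated by the published AVAS stage with the access created. The report should contain:

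- a stage-by-access table;
- overall and per-stage agreement with 95% confidence intervals;
- a flag on any stage whose commonest created access is not an indicated one.

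State which access or accesses each stage indicates before the data are analysed. Keep the fitted models for the information carried by AVAS alone and for the added value of clinical factors. Note in the interpretation that disagreement may reflect local practice.

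The cost is a sentence or two and one extra table. The vascular parameters and the created access are already collected, and patient care does not change. The downside is that the headline figure may be less favourable than a model accuracy.
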